10.5.3 Safety objectives

10.5.3.1 Analysis set and grouping for the analyses

For all safety analyses, the safety set will be used. All listings and tables will be presented by treatment group.

The overall observation period will be divided into three mutually exclusive segments:

1. pre-treatment period: from day of subject's first informed consent to the day before first administration of study treatment
2. on-treatment period: from day of first administration of study treatment to 30 days after last actual administration of the same study treatment (including start and stop date)
3. post-treatment period: starting at day 31 after last administration of any study treatment

Summary tables for safety data will be presented for the on-treatment period. Comparative analysis will be performed only for the on-treatment period. Listings of safety data will include pre-treatment, on-treatment, and post-treatment periods, with a flag to indicate data collected before or after the on-treatment period.

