7.1.4 Treatment period

There is no fixed duration of treatment planned per patient. All patients will be given the opportunity to receive study treatment until the date that corresponds to 96 weeks after the last patient receives the first study dose.

During the treatment phase, the patients will receive either ABL001 treatment 40 mg BID or bosutinib 500mg QD according to randomization. The dose can be modified, if required from the perspective of tolerance, following the guidance in [Section 6.2](#) and [Section 6.3](#). Treatment is ongoing until patient experiences unacceptable toxicity, disease progression, death, lost to follow-up and/or treatment is discontinued at the discretion of the investigator or withdrawal of consent.

The patients are advised to adhere to the food restrictions during the treatment (fasting status regarding study treatment administration, avoidance of prohibited concomitant medication).

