10.3 Treatments (study treatment, concomitant therapies, compliance)

The Safety set will be used for the analyses below.

Categorical data will be summarized as frequencies and percentages. For continuous data, mean, standard deviation, median, 25th and 75th percentiles, minimum, and maximum will be presented.

The duration of exposure in days to ABL001 and bosutinib, as well as the dose intensity (computed as the ratio of actual cumulative dose received and actual duration of exposure)

and the relative dose intensity (computed as the ratio of dose intensity and planned dose intensity) will be summarized by means of descriptive statistics.

The number of patients with dose adjustments (reductions, interruption, or permanent discontinuation) and the reasons will be summarized by treatment group and all dosing data will be listed.

Concomitant medications and significant non-drug therapies prior to and after the start of the study treatment will be listed and summarized according to the Anatomical Therapeutic Chemical (ATC) classification system, by treatment group.

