10.5 Secondary objectives

The secondary objectives in this study are as follows:

- To compare additional parameters of the efficacy of ABL001 versus bosutinib, defined as:

Key secondary endpoints

[figure not shown]
- MMR rate at 96 weeks

Other efficacy endpoints

- Cytogenetic response (Complete, Partial, Major, Minor, Minimal, no response) rate at all scheduled data collection time points including 24, 48 and 96 weeks.
 - Cytogenetic response (Complete, Partial, Major, Minor, Minimal, no response) rate by all scheduled data collection time points including, 24, 48 and 96 weeks.
 - MMR rate at all scheduled data collection time points (except 24 and 96 weeks which are already covered by primary and key secondary endpoints)
 - MMR rate by all scheduled data collection time points including 24, 48 and 96 weeks.
 - Time to MMR
 - Duration of MMR
 - Time to CCyR
 - Duration of CCyR
 - Time to treatment failure
 - Progression free survival
 - Overall survival
-
- To compare the safety and tolerability profile of ABL001 versus bosutinib
 - To characterize the PK of ABL001 in the CML-CP population

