10.5.3.2 Adverse events (AEs)

Summary tables for adverse events (AEs) will include only AEs that started or worsened during the on-treatment period, the *treatment-emergent* AEs.

The incidence of treatment-emergent adverse events (new or worsening from baseline) will be summarized by system organ class and/or preferred term, severity (based on CTCAE grades), type of adverse event, relation to study treatment.

Serious adverse events, non-serious adverse events and adverse events of special interest (AESI) during the on-treatment period will be tabulated.

All deaths (on-treatment and post-treatment) will be summarized.

All AEs, deaths and serious adverse events (including those from the pre-treatment, on-treatment and post-treatment periods) will be listed and those collected before or after the on-treatment period will be flagged.

[figure not shown]

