10.5.3.3 Laboratory abnormalities

Grading of laboratory values will be assigned programmatically as per NCI Common Terminology Criteria for Adverse Events (CTCAE) version 4.03. The calculation of CTCAE grades will be based on the observed laboratory values only, clinical assessments will not be taken into account.

CTCAE Grade 0 will be assigned for all non-missing values not graded as 1 or higher. Grade 5 will not be used.

For laboratory tests where grades are not defined by CTCAE v4.03, results will be categorized as low/normal/high based on laboratory normal ranges.

The following listings and summaries will be generated separately for hematology, and biochemistry tests:

- Listing of all laboratory data with values flagged to show the corresponding CTCAE v4.03 grades if applicable and the classifications relative to the laboratory normal ranges

For laboratory tests where grades are defined by CTCAE v4.03

- Worst post-baseline CTCAE grade (regardless of the baseline status). Each patient will be counted only once for the worst grade observed post-baseline in the on-treatment period.
- Shift tables using CTCAE grades to compare respective baseline to the worst on-treatment value

For laboratory tests where grades are not defined by CTCAE v4.03,

- Shift tables using the low/normal/high/ (low and high) classification to compare respective baseline to the worst on-treatment value.

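### The supplied text compares adverse events between arms by on-treatment incidence alone, with nothing to allow for unequal time at risk

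*Combined protocol and SAP*

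**What the plan says.** The full statistical section available is that of the Amendment 1 protocol, which calls asciminib ABL001.

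- Section 10.5 lists as a secondary objective "To compare the safety and tolerability profile of ABL001 versus bosutinib".
- Section 10.5.3.1 defines the "on-treatment period: from day of first administration of study treatment to 30 days after last actual administration of the same study treatment" and states "Comparative analysis will be performed only for the on-treatment period".
- Section 10.5.3.2 gives the adverse event (AE) measure: "The incidence of treatment-emergent adverse events (new or worsening from baseline) will be summarized by system organ class and/or preferred term, severity", and so on. Serious AEs and AEs of special interest are to be tabulated.
- Section 10.5.3.3 treats laboratory grades in the same way: "Each patient will be counted only once for the worst grade observed post-baseline in the on-treatment period".
- Section 10.5.3.5 marks supportive analyses as not applicable.
- Section 10.3 summarises "The duration of exposure in days to ABL001 and bosutinib", with dose intensity, by descriptive statistics. It does not link exposure to AE incidence.
- Section 7.1.4 states "There is no fixed duration of treatment planned per patient". Patients may be treated until 96 weeks after the last patient's first dose, and Section 7.1.6 requires discontinuation at treatment failure or disease progression.

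The Amendment 3 summary of changes lists Section 10.5.3.1 among the sections altered for the bosutinib-to-asciminib switch. The amended wording is not in the supplied text. The Amendment 2 and 3 change lists name neither Section 10.5.3.2 nor Section 10.3.

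**The concern.** The proportion of patients with at least one event grows with the time they are watched. If one arm stays on treatment longer, its crude incidence is higher even when the two drugs are equally toxic per unit of time. Here time on treatment is itself an outcome: it ends with failure, progression, toxicity or choice. The plan recognises this elsewhere, since Section 10.5.2 counts discontinuation for any reason as a treatment-failure event and compares time to treatment failure between arms.

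At stake is the reading of the safety comparison. The protocol gives learning about the safety of the experimental drug as its reason for 2:1 allocation (Section 2.2). The primary endpoint and the sample size are not affected.

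**Working it through.** **No figure to reproduce.** The documents give no AE rates, discontinuation rates or expected exposure by arm for the safety comparison. The nearest design figure is the sample size in Section 10.8. A pooled two-proportion calculation (15% versus 35%, two-sided 5%, 90% power, 2:1) reproduces it at 74 + 148 = 222, but it plays no part below.

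**Model.** Let λ be a constant AE hazard per week, identical in both arms; μ a constant discontinuation hazard per week; T the potential treatment time; and e = 30/7 = 4.29 weeks the post-dose tail from Section 10.5.3.1.

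- μ = −ln(1 − d)/T, where d is the proportion discontinued by T.
- Mean weeks on treatment = (1 − exp(−μT))/μ.
- Crude incidence = 1 − exp(−λe) × [ (μ/s)(1 − exp(−sT)) + exp(−sT) ], with s = λ + μ.

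**Inputs.** T = 96 weeks and the 30-day tail come from the protocol. The discontinuation proportions and the AE rates (0.2, 0.5 and 1.0 per patient-year, divided by 52.18 for weekly λ) are assumptions. Asciminib is placed in the longer-treated position only for illustration.

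**Worked case: 30% versus 60% discontinued, 0.2 events per patient-year.**

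- λ = 0.2/52.18 = 0.00383; exp(−λe) = 0.984.
- Longer-treated arm: μ = −ln(0.7)/96 = 0.00372; mean 0.3/0.00372 = 80.7 weeks; s = 0.00755; exp(−sT) = 0.485; bracket = 0.492 × 0.515 + 0.485 = 0.738; incidence = 1 − 0.984 × 0.738 = 27.4%.
- Shorter-treated arm: μ = −ln(0.4)/96 = 0.00954; mean 0.6/0.00954 = 62.9 weeks; s = 0.01338; exp(−sT) = 0.277; bracket = 0.713 × 0.723 + 0.277 = 0.793; incidence = 1 − 0.984 × 0.793 = 22.0%.
- Ratio 1.24, difference 5.4 points, with no true difference.

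**Range at 96 weeks.**

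| Discontinued | Mean weeks | 0.2 per year | 0.5 per year | 1.0 per year |
|---|---|---|---|---|
| 30% vs 30% | 80.7 vs 80.7 | ratio 1.00 | ratio 1.00 | ratio 1.00 |
| 30% vs 45% | 80.7 vs 72.3 | 27.4% vs 24.8%, 1.10 | 53.9% vs 49.4%, 1.09 | 76.5% vs 71.3%, 1.07 |
| 30% vs 60% | 80.7 vs 62.9 | 27.4% vs 22.0%, 1.24 | 53.9% vs 44.4%, 1.21 | 76.5% vs 65.5%, 1.17 |

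Swapping the arms inverts the ratios (1.24 becomes 1/1.24 = 0.81). The first-event rate per patient-year has ratio 1.00 in every row, because the hazard is equal by construction.

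**Masking.** If the longer-treated arm truly had 0.70 times the event rate, 30% versus 60% discontinuation gives crude ratios of 0.92, 0.95 and 1.00 at reference rates of 0.2, 0.5 and 1.0 per year. Most or all of a real advantage would not show.

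**Effect of a 24-week window.** Keep the weekly μ of the 30% versus 60% case. Discontinuation by week 24 is then 1 − 0.7^(24/96) = 8.5% versus 1 − 0.4^(24/96) = 20.5%. On-treatment events within 24 weeks follow from the same formula with T replaced by 24 − 4.29 = 19.7 weeks. Incidence is 8.5% versus 8.2%, 20.0% versus 19.1%, and 35.9% versus 34.5% at the three rates, with ratios of 1.04 to 1.05. The window removes most of the distortion, though not all of it.

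**The case against.** **Version.** The quoted analysis text is from Amendment 1, and Section 10.5.3.1 was later changed. This stands as a limit: the amended section has to be read before the point is final. The listed reason for the change is the switch design, and nothing supplied shows that an exposure adjustment was added.

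**Does exposure differ, and which way?** A reader might infer that asciminib patients must stay on treatment longer, because the plan assumes 35% versus 15% MMR and only bosutinib failures may switch. The documents do not support that step. Not being in MMR means a ratio above 0.1%, whereas molecular failure at six months means a ratio above 10%, so many non-responders need not stop. The switch option belongs to Amendment 3, not to the quoted analysis text, and failing patients must stop study treatment in either arm anyway. Table 6-2 also contains rules that could shorten asciminib exposure: Grade 4 non-hematologic reactions require permanent discontinuation on asciminib but hold and reduction on bosutinib, and the Grade 3 and 4 diarrhea rows also differ. The direction is open.

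**Size.** Larger gaps can be produced. Giving every patient a mean exposure of 1.8 versus 0.8 years at a hazard of 0.5 per year yields 1 − exp(−0.90) = 59.3% versus 1 − exp(−0.40) = 33.0%, or 26 points. Those exposures come from no document, and assigning everyone the mean ignores variation between patients.

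**Descriptive use.** On-treatment incidence is a legitimate descriptive measure, no safety test is specified, and the exposure summary would reveal an imbalance. All true. But revealing an imbalance does not correct for it, and the objective is worded as a comparison. That the incidence is crude is inferred from the absence of any person-time denominator.

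**Conclusion.** The point holds as a gap in the supplied text: the between-arm safety comparison rests on incidence over a window of patient-dependent length, with no method to separate event rate from time at risk. If exposure differs, the longer-treated arm will look worse than it is. The documents do not establish that exposure will differ, nor in which direction, so it would be wrong to conclude that the planned tables are biased against asciminib.

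Under a constant hazard and the assumed discontinuation proportions, the crude ratio departs from 1.00 by 7% to 24% at 96 weeks, and not at all when discontinuation is equal. This is a worthwhile, inexpensive improvement to the safety analysis, subject to checking the amended Section 10.5.3.1.

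**What to change.** First check the amended Section 10.5.3.1 and any separate SAP text. If exposure adjustment is already there, a cross-reference closes the point. If not:

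- Keep the crude on-treatment tables.
- For AEs, serious AEs and AEs of special interest, pre-specify the first-event incidence per 100 patient-years at risk, by arm, with 95% confidence intervals. Time at risk runs from first dose to first event or the end of the on-treatment period.
- Add a fixed-window table of events in the first 24 weeks.

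Both additions are needed. Patient-year rates assume a roughly constant hazard and can favour the longer-treated arm if events cluster early; the 24-week table covers that case.

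The cost is a few more tables from dosing and AE dates already collected, with no change to conduct, sample size or primary endpoint. Specify them in advance: in an open-label trial, an adjustment chosen after exposure is known would look selective.

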10.5.3.2 Adverse events (AEs)

Summary tables for adverse events (AEs) will include only AEs that started or worsened during the on-treatment period, the *treatment-emergent* AEs.

The incidence of treatment-emergent adverse events (new or worsening from baseline) will be summarized by system organ class and/or preferred term, severity (based on CTCAE grades), type of adverse event, relation to study treatment.

Serious adverse events, non-serious adverse events and adverse events of special interest (AESI) during the on-treatment period will be tabulated.

All deaths (on-treatment and post-treatment) will be summarized.

All AEs, deaths and serious adverse events (including those from the pre-treatment, on-treatment and post-treatment periods) will be listed and those collected before or after the on-treatment period will be flagged.

[figure not shown]
10.5.3.3 Laboratory abnormalities

Grading of laboratory values will be assigned programmatically as per NCI Common Terminology Criteria for Adverse Events (CTCAE) version 4.03. The calculation of CTCAE grades will be based on the observed laboratory values only, clinical assessments will not be taken into account.

CTCAE Grade 0 will be assigned for all non-missing values not graded as 1 or higher. Grade 5 will not be used.

For laboratory tests where grades are not defined by CTCAE v4.03, results will be categorized as low/normal/high based on laboratory normal ranges.

The following listings and summaries will be generated separately for hematology, and biochemistry tests:

- Listing of all laboratory data with values flagged to show the corresponding CTCAE v4.03 grades if applicable and the classifications relative to the laboratory normal ranges

For laboratory tests where grades are defined by CTCAE v4.03

- Worst post-baseline CTCAE grade (regardless of the baseline status). Each patient will be counted only once for the worst grade observed post-baseline in the on-treatment period.
- Shift tables using CTCAE grades to compare respective baseline to the worst on-treatment value

For laboratory tests where grades are not defined by CTCAE v4.03,

- Shift tables using the low/normal/high/ (low and high) classification to compare respective baseline to the worst on-treatment value.

10.5.3.4 Other safety data

ECG

ECGs (12-lead) including PR, QRS, QT, QTcF, and HR intervals will be obtained for each subject during the study. ECG data will be read and interpreted centrally.

Categorical analysis of QT/QTc interval data based on the number of patients meeting or exceeding predefined limits in terms of absolute QT/QTc intervals or changes from baseline will be presented. In addition, a listing of these patients will be produced by treatment group.

Vital signs

Data on vital signs will be tabulated and listed, notable values will be flagged.

10.5.3.5 Supportive analyses for secondary objectives

Not applicable.

10.5.3.6 Tolerability

Tolerability of each study treatment will be assessed by summarizing the number of subjects with dose interruptions and dose reductions. Reasons for dose interruptions and dose reductions will be listed by subject and summarized.

10.5.4 Secondary PK objectives

The PK objective is to characterize the PK of ABL001 in CML population.

Using PAS, summary statistics (n, mean, SD, coefficient of variation (CV) for mean, geometric mean, CV for geometric mean, median, minimum and maximum) will be presented for plasma concentration at each scheduled time point. The geometric mean with mean (SD) and individual plasma concentration versus time profiles of ABL001 will be displayed graphically.

Using Safety set, concentration data will be listed. Concentration values below the limit of quantification (BLQ) will be set to zero by the Bioanalyst and displayed in listings as zero

with a flag. BLQ values will be handled as zero in any calculations of summary statistics, but handled as missing for the calculation of the geometric means and CVs.

Pharmacokinetic parameters will be determined by non-compartmental method(s) using the pharmacokinetic profile of ABL001 in patients with full PK sampling. PK parameters listed in [Table 10-1](#) will be derived and reported, when feasible.

Population PK modeling may be performed and the results may be reported in a separate population PK report. Data from this study may be combined with data from other studies for this analysis.

Table 10-1 Non compartmental pharmacokinetic parameters in full PK group

AUC _{0-12h}	The area under the plasma concentration-time curve from time zero to 12 h (mass x time x volume ⁻¹) ^a
C _{max}	The maximum (peak) observed plasma drug concentration after dose administration (mass x volume ⁻¹)
T _{max}	The time to reach maximum (peak) plasma drug concentration after dose administration (time)
CL/F	The total body clearance of drug from the plasma after oral administration (volume x time ⁻¹)

[figure not shown]
10.6 Exploratory objectives

10.6.1 Exploratory efficacy objectives

- To evaluate the influence of factors such as major cytogenetic status at baseline, failure/intolerance to prior TKIs, line of therapy, gender, race and age on the effect of ABL001 with respect to the primary efficacy endpoint.
- To characterize mutations in the BCR-ABL1 gene at baseline and at end of treatment and examine their association with molecular and cytogenetic response for ABL001 vs bosutinib

10.6.1.1 Data analysis of exploratory efficacy objectives

Subgroup analyses will be performed to evaluate the influence of factors such as baseline major cytogenetic response status, baseline BCR-ABL ATP-binding site mutation status (from local historical record and from Sanger Sequencing), failure/intolerance to prior TKIs, line of therapy, gender, race and age on the primary efficacy endpoint. In addition, a logistic regression analysis will incorporate the key baseline variables into the model to further evaluate the impact of these variables on the primary endpoint and to provide a treatment effect estimate which is adjusted for imbalances in the treatment groups. An adjusted odds ratio for the treatment effect with associated 95% confidence intervals will be presented. Mantel-Haenszel estimates of the common odds ratio and the corresponding 95% confidence interval will also be provided.

10.6.2 Exploratory PK objectives

The potential relationship between ABL001 exposure (e.g. trough concentration) and efficacy or safety endpoints may be assessed by graphic exploration and/or statistical modeling as appropriate. The details will be further specified in the SAP. Additional exposure-response analyses for ECG may be conducted and reported separately.

10.6.3 Exploratory biomarker objectives

The study is not powered to assess specific biomarker-related hypotheses, thus the statistical analyses of these data should be considered exploratory in nature. Analytical results from such analyses may be used to generate additional hypotheses that must then be verified with data derived from subsequent clinical trials. Furthermore, additional post hoc exploratory assessments may be performed.

While the goal of the biomarker analyses is to provide supportive data for the clinical study, there may be circumstances when a decision is made to stop a sample collection, or not perform/ discontinue the analysis of blood and bone marrow (e.g. issues related to the quality and or quantity of samples, or issues related to the assay that preclude the analysis of samples). Under such circumstances, the number of samples may be inadequate to perform a rigorous data analysis and the available data will only be listed.

Unless otherwise specified, all statistical analyses of biomarker data will be performed on subjects with valid biomarker samples.

The exploratory biomarker objectives are:

- To characterize mutations in the BCR-ABL1 gene at baseline, upon loss of molecular response and at end of treatment and examine their association with molecular and cytogenetic response for ABL001 vs. bosutinib
- [REDACTED]
- [REDACTED]
- To assess clonal evolution of pre-existing mutations versus mutations acquired during treatment with ABL001 vs. bosutinib

[REDACTED]

[REDACTED]

[REDACTED]

[REDACTED]

- Explore the relationship between BCR-ABL1 mutations at baseline and efficacy outcomes for the primary endpoint and key secondary endpoints. The association between loss of response and BCR-ABL1 mutations will also be explored descriptively.
- Explore the influence of early molecular response levels on long term molecular response

[REDACTED]

Additional exploratory biomarker analyses may be performed depending on the data. All patients with evaluable biomarker measurements in the FAS will be included in the analysis and will be reported in a separate biomarker report.

